9.1.2. Sensitivity Analyses of the Primary Efficacy Endpoint

Sensitivity analysis using Single Imputation: For subjects without post-randomization ESS data, the result from the end of the SDP will be carried forward (i.e. Baseline observation Carried Forward [BOCF] approach) and analyzed as described section 9.1.1.

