6.16.2. Handling of Early Terminations

If a subject terminates early from the study, either at his or her request or at the Investigator's discretion, the Investigator will record the reason(s) for Early Termination on the relevant eCRF page and notify the Sponsor/designee immediately.

- For all subjects who prematurely discontinue during the Double-blind Randomized Withdrawal Period, an attempt should be made to perform all procedures associated with the End of Double-blind Randomized Withdrawal Visit.

Clinical Study Protocol: JZP080-301 Amendment 2

- For all subjects who prematurely discontinue during periods other than the Double-blind Randomized Withdrawal Period, an attempt should be made to perform procedures associated with the End of Open-label Extension Visit.

It is vital to obtain follow-up data on any subject who terminated because of an AE, abnormal laboratory test, or ECG finding. In any case, every effort must be made to undertake safety follow-up procedures.

All subjects who early terminate from the study within 2 weeks of receiving the last dose should be asked to return 2 weeks later for the Safety Follow-up Visit.

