7.4.1. Double-blind Randomized Withdrawal Week 1 Phone Contact

- Discuss dosing with the subject and confirm compliance; confirm that the Dosing Diary is being completed.
- Administer the C-SSRS Since Last Visit version.
- Record all AEs that occurred since the last visit and follow up on any AEs that were ongoing at the last visit.
- Record all concomitant medications that were taken since the last visit.
- Schedule the End of Double-blind Randomized Withdrawal Period clinic visit.

7.4.2. End of Double-blind Randomized Withdrawal Visit (and Early Termination Visit for Subjects Discontinuing during the Double-blind Randomized Withdrawal Period)

- Obtain weight in ordinary indoor clothes (without shoes).
- Obtain vital signs (systolic and diastolic blood pressure, heart rate and respiratory rate, and body temperature), in the seated position after the subject has been resting for 5 minutes.
- Obtain urine sample for a drug screen and a pregnancy test for all females of childbearing potential.
- Perform breath alcohol test.
- For subjects who early terminate due to an AE only: obtain a 12-lead ECG after the subject has been resting supine for at least 5 minutes.
- For all subjects who early terminate: perform a full PE (excluding genitourinary exam) with brief neurological exam
- Collect sleep diary and VAS for sleep inertia. Review with the subject and confirm that both were completed.
- Administer:
 - ESS ([Appendix 7](#))
 - CGIc (compared with end of Stable Dose Period version; [Appendix 14](#))
 - PGIC (compared with end of Stable Dose Period version; [Appendix 9](#))
 - IHSS ([Appendix 11](#))
 - FOSQ-10 ([Appendix 15](#))
 - WPAI:SHP ([Appendix 16](#))
 - C-SSRS Since Last Visit version ([Appendix 6](#))
- Discuss dosing with the subject and confirm compliance; confirm that the Dosing Diary is being completed.
- Record all AEs that occurred since the last visit and follow up on any AEs that were ongoing at the last visit.
- Record all concomitant medications that were taken since the last visit.
- Collect study drug dispensed at the End of Stable Dose Visit and assess compliance.
- Access IWRS and dispense study drug.
- Schedule the Open-label Extension Week 2 clinic visit.

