Modified Intent-to-Treat	
The mITT Analysis Set (mITT) will include all subjects who are randomized to JZP-258 or Placebo, who received at least 1 dose of study drug during the DBRW and have at least one set of post randomization assessments for ESS or IHSS, or a PGIc value at end of DBRW.
 
A set of post randomization assessments is defined as having an end of SDP and end of DBRW value for ESS or IHSS. The mITT includes subjects with any primary or key secondary endpoint data.
 
This analysis set will be used for analyzing efficacy endpoints (primary,

Analysis Set	Description
	secondary, and exploratory). Demographics and other baseline characteristics data, past medical conditions/diseases, surgical history, and IH Diagnosis IH diagnosis history data will also be summarized using this analysis set. For summaries and analyses based on the mITT, subjects will be classified according to randomized treatment group.
PK	The PK Analysis Set will consist of all subjects who received JZP-258 and have any evaluable PK data from at least 1 post dose sample. This analysis set will be used for summarizing the Pharmacokinetic data. Demographic and other baseline characteristics data, as well as exposure to study drug will be summarized.

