7.2.5. Missing and Partial Data

Missing or partially missing concomitant medications and AEs start and stop dates will be imputed as described in **Error! No bookmark name given..** However, imputed dates will NOT be presented in the listings as their sole purpose will be for the classification of the medications as past, concomitant or post (refer to section 8.5) and the classification of the AEs as prior,

treatment-emergent or post (refer to section 10.2).

Missing questionnaire data will be handled as described in the following sections:

- ESS:
 - Individual item scores: section 9.1
 - Total score: section 9.1.2
- Missing data will not be imputed for key secondary endpoints, secondary endpoints, and other secondary endpoints. The handling of missing individual items for IHSS is summarized section 9.2.2. For TST and VAS, daily averages are calculated among non-missing records. Only if all daily values are missing for the last week of the SDP or DBRW, then the subject will be excluded from the comparative efficacy analysis for these endpoints.
- Missing safety data will not be imputed except for AEs and concomitant medication start and stop dates as described above.

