9. EFFICACY

Unless otherwise described, efficacy data will be primarily presented by randomized treatment group using mITT, and treatment comparison will be between the randomized treatment groups, JZP-258 and placebo.

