9.1.1. Primary Endpoint Analysis

For the main analysis of the primary efficacy endpoint, an analysis of covariance (ANCOVA)

will be performed using the PROC MIXED SAS procedure. The model will include the change in ESS from the end of the SDP to the end of the DBRW as the dependent variable; the treatment group and baseline medication group as fixed effects as well as the ESS score at the end of SDP as a covariate. If the ESS total score at the SDP and/or DBRW is still missing after the imputation of ESS item value as specified above, the subject will be excluded from the primary analysis.

All group comparisons from the ANCOVA model will be based on Type III sum of squares. Least square mean (LS mean) and standard error (SE) will be provided for each treatment group. The difference between these two LS means along with the SE of the difference, 95% confidence interval (CI) and associated p-value corresponding to testing the hypothesis of no difference between the treatment groups will also be provided.

The normality assumption of the ANCOVA model will be examined by residual analysis using the Shapiro- Wilk test at a 0.05 significance level. If the normality assumption is considered violated, a non-parametric ANCOVA with the covariate and response variables replaced by their ranks (Conover and Iman 1982) will be used for the primary efficacy analysis of the primary efficacy endpoint. In the event of ties in the baseline or change from baseline, average ranks will be used. The ranks will be used in the ANCOVA with the rank for the change from baseline as the dependent variable, treatment and baseline medication group as fixed effects, and the rank for ESS score at the end of SDP as a covariate. P-values will be presented from the rank based ANCOVA. The estimated median difference between the change in ESS between the two treatment groups and asymptotic 95% confidence intervals will be presented using the Hodges- Lehman estimator (Hodges and Lehman 1962).

A box plot of the change in ESS from the end of the SDP to the end of DBRW by randomized treatment group will be presented.

Example SAS Code for the ANCOVA model is shown below.

PROC MIXED DATA =ANAL METHOD =TYPE3;

CLASS TRT03PN BMED;

MODEL CHG = TRT03PN BASE BMED/ RESIDUAL OUTP=RESIDUAL;

LSMEANS TRT03PN/DIFF CL;

RUN;

The SAS code below evaluates the assumption of normality for the residuals from the above ANCOVA model using the Shapiro Wilk test.

PROC UNIVARIATE DATA=RESIDUAL NORMAL;

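### The missing-data sensitivity analyses promised for PGIc and IHSS are not in the SAP, and the one ESS check, run on the mITT set, nearly repeats the primary analysis

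*SAP*

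**What the plan says.** **The commitment.** Protocol 9.6 bases the primary analysis on mITT and leaves to the SAP the definition of sensitivity analyses for missing values, for the primary and key secondary endpoints alike. Protocol 11.6 requires changes to planned analyses to be documented in the SAP.

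**Key secondary endpoints.** SAP 7.2.5 states: "Missing data will not be imputed for key secondary endpoints, secondary endpoints, and other secondary endpoints". SAP 9.2.1 (PGIc) has no missing-data analysis. SAP 9.2.2 (IHSS) has an item-level rule for fewer than four missing items; with four or more missing, the total is missing. SAP 7.6 lists three changes: the interim analysis not done, the wording on 140 subjects, and COVID-19.

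**ESS.** In the primary ANCOVA (SAP 9.1.1), if the total score is missing at either visit, "the subject will be excluded from the primary analysis". SAP 7.2.5 routes missing ESS data by level, the last entry being "Total score: section 9.1.2". Section 9.1.2 holds a single baseline-observation-carried-forward (BOCF) analysis: "For subjects without post-randomization ESS data, the result from the end of the SDP will be carried forward". It names no analysis set, but Section 9 supplies one: "Unless otherwise described, efficacy data will be primarily presented by randomized treatment group using mITT".

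**mITT entry.** Besides randomisation and a double-blind dose, SAP 6 requires a set of assessments or an end-of-period PGIc. "A set of post randomization assessments is defined as having an end of SDP and end of DBRW value for ESS or IHSS".

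**When the scales are collected.** ESS, PGIc and IHSS are all given at one visit, headed in Protocol 7.4.2 "End of Double-blind Randomized Withdrawal Visit (and Early Termination Visit for Subjects Discontinuing during the Double-blind Randomized Withdrawal Period"). For early terminations, Protocol 6.16.2 says: "For all subjects who prematurely discontinue during the Double-blind Randomized Withdrawal Period, an attempt should be made to perform all procedures".

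**The concern.** PGIc and IHSS are the second and third tests in the confirmatory hierarchy (SAP 7.4). A claim on either would rest on complete cases, with no planned check on the losses, although the protocol said that one would be defined.

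For ESS a check exists, but the subjects who matter most to it are those who were randomised and dosed and then gave no end-of-period data. They are removed before the check is run. A reader who sees the primary and sensitivity results agree may take this as robustness, when the two analyses use almost the same subjects. SAP 8.1 and 8.2 will show by arm how many subjects were lost, but not what the losses do to the estimates.

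**Working it through.** **1. Who the ESS check can reach on mITT**

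| End-of-period data (randomised and dosed) | In mITT | In primary ANCOVA | Changed by BOCF |
|---|---|---|---|
| ESS total present | yes | yes | no |
| ESS missing; IHSS pair or PGIc present | yes | no | yes |
| None of the three | no | no | no |

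Only the middle row differs between the two analyses. Because the three scales share a visit, that row should be nearly empty, though not empty by construction: three or more missing ESS items leave no total (SAP 9.1). Even there the wording is unclear. Section 9.1.2 is triggered by having no post-randomisation ESS data, whereas 7.2.5 sends it a missing total score.

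**2. The plan's own figure**

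Inputs from SAP 5.4: 56 per arm, difference 3.5, SD 5.5, two-sided 0.05, one O'Brien-Fleming-type interim at 60% information. The expected z is 3.5 / (5.5 × √(2/56)) = 3.37. Fixed-design power is 92.0%; with the interim it is 91.84%, against 91.8% stated. Enrolment is 112 / 0.8 = 140. That 20% loss is before randomisation; no later rate is given, so the loss counts below are assumptions.

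**3. BOCF extended to all randomised, dosed subjects**

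Take an observed JZP-258 mean change of 0, a placebo mean of d, and no covariate adjustment. Let mA and mP be the JZP-258 and placebo losses.

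- Complete case: z = d / (5.5 × √(1/(56−mA) + 1/(56−mP))).
- BOCF: estimate d × (56−mP)/56. The variance in an arm with m losses and observed mean μ is 5.5² × (55−m)/55 + (m/56)(1−m/56)μ². The standard error is the square root of the sum of the two variances divided by 56.

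At d = 3.5:

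| Losses | Complete-case z | BOCF estimate | BOCF z |
|---|---|---|---|
| 6 placebo | 3.27 | 3.125 | 3.06 |
| 6 JZP-258 | 3.27 | 3.500 | 3.46 |
| 6 in each arm | 3.18 | 3.125 | 3.15 |

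Zero change means no worsening. That is strict for a placebo loss and generous for a JZP-258 loss.

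**4. A less favourable assumption for lost JZP-258 subjects**

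Give the m lost JZP-258 subjects the placebo mean. The estimate is d(1−m/56), and the JZP-258 variance is 5.5² + (m/56)(1−m/56)d². For m = 2, 3 and 6 at d = 3.5, z is 3.24, 3.17 and 2.98, against complete-case values of 3.34, 3.32 and 3.27. To bring z to 1.96, the lost subjects would need a mean worsening of 28.8, 20.9 and 11.7 points. The first exceeds the 0–24 range of the scale.

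The conclusion differs only if the observed difference falls between the two significance thresholds: about 2.06–2.12, 2.07–2.16 and 2.10–2.29. If the planning effect is true, the chance of that is 0.9%, 1.4% and 3.4%. At d = 2.2 the complete-case p is 0.036, 0.037 and 0.040, and the placebo-mean p is 0.042, 0.046 and 0.060, so only six losses cross 0.05. With six placebo losses instead, BOCF gives p = 0.053 against 0.040.

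**5. PGIc**

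The documents give no planning rates, so these counts are assumed (JZP-258 vs placebo; one-stratum CMH; missing counted as worse).

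| Observed | p | Missing as worse | p |
|---|---|---|---|
| 15/53 vs 28/56 | 0.021 | 18/56 vs 28/56 | 0.056 |
| 15/53 vs 27/53 | 0.018 | 18/56 vs 30/56 | 0.023 |
| 16/53 vs 34/56 | 0.0015 | 19/56 vs 34/56 | 0.0047 |

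Only the first row changes conclusion. It needs a modest effect and all three losses on JZP-258.

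**The case against.** **The analysis set is given.** A reader might infer from the silence of SAP 9.1.2 that its analysis set is undefined, or that it means all randomised subjects. The documents do not support that. Section 9 and the mITT definition make mITT the set for efficacy, and the Randomized set is assigned only to disposition. This stands, so the BOCF figures on all randomised, dosed subjects describe a possible extension, not the plan.

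**BOCF does not simply favour the drug.** A reader might infer that it does from the JZP-258-only case. With placebo losses it is stricter than complete case, and with equal losses it is about neutral. This stands too.

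**The check is not empty, and losses are limited.** ESS, IHSS and PGIc are separate forms, so one can be lost alone. The double-blind period lasts two weeks, and early terminators should be offered the full visit. This limits the size of the problem, but the protocol asks only for an attempt, so complete losses remain possible.

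**The SAP states its decision.** Section 7.2.5 says openly that key secondary data are not imputed, and Protocol 11.6 does not name Section 7.6 as the place for changes. But a no-imputation rule is not a sensitivity analysis. The IHSS item rule is scoring, and the on-site versus remote subgroup does not address missing data. The commitment in 9.6 is unmet, and the section that sets out the changes from the protocol omits it.

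**The proposed methods are not promised.** Neither document mentions reference-based imputation, tipping point or missing counted as worse. They are recommendations, and leaving mITT would itself depart from Protocol 9.4.

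**Conclusion.** The point holds as a gap between protocol and SAP plus a weak check. The missing PGIc and IHSS analyses, and their absence from SAP 7.6, follow from the text with no assumption. That the ESS check is nearly empty follows from the mITT definition and the shared visit.

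The numerical consequence is small for ESS. At planning values no loss pattern examined brings z below 2.9, and a changed conclusion needs a borderline observed difference. PGIc could be more exposed, but only under assumed rates and one-sided losses. All sizes rest on assumed loss counts. A reader might infer that the primary conclusion is unsafe; the figures do not support that. The plan should be changed, because agreement between the two ESS analyses would say little and PGIc and IHSS have no check at all.

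**What to change.** Before the unblinding described in SAP 5.6:

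- **(a)** In SAP 9.1.2, run the missing-data sensitivity analysis on all randomised and dosed subjects, and have it apply whenever the end-of-period ESS total score is missing, in line with 7.2.5.
- **(b)** For ESS and IHSS, add one analysis with a less favourable assumption for missing JZP-258 subjects: reference-based imputation from placebo, or a tipping-point series. Keep BOCF as a supplement on the same set.
- **(c)** For PGIc, add an analysis that counts missing as worse in both arms.
- **(d)** In SAP 7.6, list the use of a set other than mITT for these analyses as a departure from Protocol 9.4. Also list, with the reason, any key secondary sensitivity analysis that will not be done.

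The cost is SAP wording and a few extra programs. The primary analysis, alpha and data collection do not change. The sensitivity estimates may come out slightly less favourable than the primary one.

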9.2. Key Secondary Efficacy Endpoints and Analyses

9.2.1. PGIc

The first key secondary efficacy endpoint is defined as the proportion of subjects reporting worsening of symptoms (minimally, much or very much worse) on PGIc at the end of the DBRW. The PGIc is a 7-point Likert-type rating scale and a widely used assessment to assess efficacy in clinical drug trials. At the end of the DBRW, subjects will rate the change in their

condition on a 7-point scale ranging from 1 = “very much improved” to 7 = “very much worse” since the end of the SDP.

The proportion of subjects reporting worsening of symptoms on PGIC will be compared between treatment groups using the Cochran-Mantel-Haenszel (CMH) test (based on the PGIC binary endpoint) stratified by baseline medication group. The point estimate and continuity corrected Wilson’s 95% CI (as modified by Newcombe) for the difference of the proportion will also be provided.

Example SAS Code for the obtaining the CMH test p-value, point estimate and 95% CI for the difference in proportion is shown below.

```
PROC FREQ DATA=ANAL;
```

```
TABLES BMED*TRT03PN*AVALCAT1/CMH;
```

```
RUN;
```

```
PROC FREQ DATA=ANAL;
```

```
TABLES TRT03PN *AVALCAT1/RISKDIFF(CL=(WILSON(CORRECT)));
```

```
RUN;
```

9.2.2. Change in IHSS

The next key secondary efficacy endpoint is the change in total IHSS score from the end of the SDP to the end of the DBRW. The IHSS is a 14-item self-reported questionnaire that assesses the severity of IH (Dauvilliers et al 2019). Questions capture symptoms of excessive sleepiness, sleep inertia, and sleep duration. Symptom frequency, intensity, and consequences are rated using a 3- or 4-point Likert scale, providing total scores that range from 0 to 50. Higher scores indicate more severe and frequent symptoms.

The IHSS total score is the sum of the 14 item-scores. Item 14 will be scored as “0” (no problem) for subjects who indicate they do not drive. If four or more item scores are missing at a specific time point, the IHSS total score will be set to missing. If less than four IHSS item scores are missing at a specific time point, then impute each missing item by multiplying the missing item’s maximum response value by the average of the remaining non-missing items proportion of maximum response.

Let Q_i be the score and M_i be the maximum possible score for each of the observed responses for the 14 items $i \in \Psi = \{1, 2, \dots, 14\}$. If the total number of items missing are less than 4 ($N < 4$) and M_j represents the maximum score for the missing item, then the score for each missing item $Q_j, j \in \Omega = \{l_1, l_2, \dots, l_N\}$, will be imputed as

$$Q_j = M_j * \left(\sum_{i \in \Psi} Q_i / M_i \right) / (14 - N) \quad j \in \Omega$$

Note that the maximum possible score can be either 3 or 4 depending on the specific question. The IHSS total score will be then calculated as the sum of the observed and imputed item scores as follows:

$$S = \sum_{i \in \Psi \setminus \Omega} Q_i + \sum_{j \in \Omega} Q_j$$

The change in IHSS total score will be summarized and analyzed similarly to the primary efficacy endpoint (refer to section 9.1.1 for details on the model and SAS code).

Two additional scores will be calculated from the IHSS questionnaire based on the following items:

- Component I is composed of five items focusing on “Night/Inertia” (Questions 1, 2, 3, 4 and 8)
- Component II includes nine items focusing on “Day/Performances” (Questions 5, 6, 7, 9, 10, 11, 12, 13 and 14)

The change in each IHSS Component will be analyzed similarly to the primary efficacy endpoint. Analysis of IHSS Components I and II are considered exploratory.

9.3. Secondary Efficacy Endpoints and Analyses

9.3.1. CGIc

The next secondary efficacy endpoint is defined as the proportion of investigators reporting worsening of symptoms (minimally, much or very much worse) on CGIc at the end of the DBRW. The CGIc is a 7-point Likert-type rating scale and a widely used assessment to assess efficacy in clinical drug trials. At the end of the DBRW, investigators will rate their impression of any change in severity of the subject’s condition on a 7-point scale ranging from 1 = “very much improved” to 7 = “very much worse” since the end of the SDP.

The proportion of subjects reporting worsening of symptoms on CGIc will be compared between treatment groups using the Cochran-Mantel-Haenszel (CMH) test stratified by baseline medication group. The point estimate and continuity corrected Wilson’s 95% CI (as modified by Newcombe) for the difference of the proportion will also be provided.

9.3.2. Change in total FOSQ-10 score

The next secondary efficacy endpoint is the change in total FOSQ-10 score from the end of the SDP to the end of the DBRW. The FOSQ-10 is a short version of the original FOSQ-30 instrument, which is a disease specific quality of life questionnaire to determine functional status in adults. Measures are designed to assess the impact of disorders of excessive sleepiness on

multiple activities of everyday living and the extent to which these activities are improved by effective treatment (Chasens 2009 and Weaver et al 1997).

The questionnaire has a 4-point Likert response format (e.g., 1= extreme difficulty, 2= moderate difficulty, 3=a little difficulty, and 4 =no difficulty). A response alternative is also available for respondents to indicate they do not do the activity for other reasons. FOSQ-10 total score is calculated by first taking the mean of the items for each subscale with more than 1 item completed and then taking the mean across the non-missing 5 subscales (General Productivity, Activity Level, Vigilance, Social Outcomes, Intimacy and Sexual Relationship) multiplied by 5. Score range is 5–20 points, with higher scores indicating better functional status.

Missing responses, and responses from activities in which the respondent does not do that activity for other reasons are not included in the score calculation (i.e., not included in the calculation of average value for subscales). Therefore, missing responses do not necessarily prevent score calculation.

The change in FOSQ-10 total score will be summarized and analyzed similarly to the primary efficacy endpoint (refer to section 9.1.1).

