6.14.6. Functional Outcomes of Sleep Questionnaire Short Version

The Functional Outcomes of Sleep Questionnaire (FOSQ) is a 30-item disease-specific quality of life questionnaire to determine functional status in adults; measures are designed to assess the impact of disorders of excessive sleepiness on multiple activities of everyday living and the extent to which these activities are improved by effective treatment ([Appendix 15](#); [Weaver 1997](#)). The FOSQ-10 is a short version of the original 30-item FOSQ that has been shown to perform similarly to the longer version ([Chasens 2009](#)). The FOSQ-10 has been shown to exhibit high internal consistency, effect sizes and pre- and post-treatment differences that are highly correlated with the longer version ([Chasens 2009](#)).

Subjects will complete the FOSQ-10 at the Baseline Visit, at the End of Stable Dose Visit, at the End of Double-blind Randomized Withdrawal Visit, and at clinic visits during the Open-label Safety Extension Period (Weeks 6, 14, and the End of Open-label Extension Visit/Early Termination).

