2. Have you generally had difficulty remembering things, because you are sleepy or tired?

			
--------------------------	--------------------------	--------------------------	--------------------------

3. Have you had difficulty operating a motor vehicle for short distances (less than 100 miles) because you become sleepy or tired?

				
--------------------------	--------------------------	--------------------------	--------------------------	--------------------------

4. Have you had difficulty operating a motor vehicle for long distances (greater than 100 miles) because you become sleepy or tired?

				
--------------------------	--------------------------	--------------------------	--------------------------	--------------------------

Jazz 14-003 JZP 110	Jazz Pharmaceuticals, Inc Assessment: Functional Outcomes of Sleep Questionnaire Short Form (FOSQ)	Version Date
		02APR2015
Visit	Subject ID	Subject Initials

(0) I don't do this activity for other reasons	(4) No difficulty	(3) Yes, a little difficulty	(2) Yes, moderate difficulty	(1) Yes, extreme difficulty
---	----------------------	---------------------------------	---------------------------------	--------------------------------

5. Have you had difficulty visiting with your family or friends in their home because you become sleepy or tired?

6. Was your relationship with family, friends or work colleagues affected because you were sleepy or tired?

7. Did you have difficulty watching a movie or videotape because you become sleepy or tired?

8. Did you have difficulty being as active as you want to be in the evening because you were sleepy or tired?

9. Did you have difficulty being as active as you want to be in the morning because you were sleepy or tired?

(0) I don't engage in sexual activity for other reasons	(4) No	(3) Yes, a little	(2) Yes, moderately	(1) Yes, extremely
--	-----------	----------------------	------------------------	-----------------------

10. Was your desire for intimacy or sex affected because you were sleepy or tired?

Subject Initials: _____

Date: _____

Thank you for completing this questionnaire.

**APPENDIX 16. WORK PRODUCTIVITY AND ACTIVITY IMPAIRMENT
QUESTIONNAIRE: SPECIFIC HEALTH PROBLEM
(WPAI:SHP)**

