5.6. Timing of analyses

The final comparative efficacy analysis for this study will occur after all randomized subjects complete or discontinues the DBRW period. For these analyses, a formal database snapshot including data per a cut-off date is planned, which will occur after the last randomized subject completes or discontinues the DBRW period. Unblinding will occur after the data extraction is completed. This analysis will include results on the final comparative analyses of efficacy end points and all available safety, open-label efficacy, and pharmacokinetic data. These results will be summarized in an interim CSR.

A final analysis will occur after all subjects complete or discontinue from the study. These analyses will be based on a locked database and will include final summaries across the study on safety, open-label efficacy, and pharmacokinetic results. Results will be summarized in a final CSR.

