7.4. Level of Significance & Multiplicity Adjustment

A hierarchical testing strategy will be implemented to preserve the family-wise Type 1 error rate at the 0.05 significance level for 2-sided testing of the primary and key secondary endpoints. The primary endpoint analysis will serve as the gatekeeper for sequentially testing the key secondary endpoints in the order (PGIC and IHSS). If the primary null hypothesis is rejected, then PGIC will be tested and if both null hypotheses for ESS and PGIC are rejected then IHSS will be tested. All tests will be 2-sided.

All other secondary endpoints, subgroup, and sensitivity analyses will be tested without multiplicity adjustments and nominal p-values will be provided.

Available safety data will also be summarized at the time of the final efficacy analysis. No statistical inferences are planned to be performed on any safety data.

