9.4.5. Open-Label Efficacy Outcomes and Analyses

Efficacy data (ESS, PGIC, IHSS, FOSQ-10, VAS, Sleep diary, and WPAI:SHP) is collected across the study; refer to the schedule of events for further information on the collection schedule for these outcomes. All data will be summarized (per similar derivations as indicated in the above corresponding endpoint sections) using descriptive statistics by time point according to baseline medication group using the SAF.

At each time point, the change from the beginning of the OTTP or screening, as appropriate, will also be reported for ESS, IHSS, FOSQ-10, VAS (last week of screening), TST (last week of screening), and WPAI:SHP.

Efficacy data will be plotted in a figure by time point across the study according to baseline medication group and overall SAF across the study. Additionally, figures by time point through the DBRW by randomized treatment group will be provided for ESS and IHSS.

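### The FOSQ-10 scoring rule in SAP 9.3.2, applied as written, can never score the one-item Intimacy subscale that it counts among the five

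*SAP*

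**What the plan says.** FOSQ-10 total score, as change from the end of the Stable Dose Period to the end of the Double-blind Randomized Withdrawal Period (DBRW), is one of two other secondary efficacy endpoints (SAP 4.2.2.2).

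SAP 9.3.2 gives the derivation in one sentence with two steps. The first is "taking the mean of the items for each subscale with more than 1 item completed". The second is "then taking the mean across the non-missing 5 subscales (General Productivity, Activity Level, Vigilance, Social Outcomes, Intimacy and Sexual Relationship) multiplied by 5". Items are scored 1 to 4 and the stated range of the total is 5 to 20. The section adds that missing answers, and "responses from activities in which the respondent does not do that activity for other reasons are not included in the score calculation".

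Protocol Appendix 15 reproduces the ten-item form. Item 10, "Was your desire for intimacy or sex affected because you were sleepy or tired", is the only item on intimacy or sex. It is printed alone under its own response header, which includes a not-applicable option.

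SAP 9.4.5 reuses the derivation for the open-label summaries: "All data will be summarized (per similar derivations as indicated in the above corresponding endpoint sections) using descriptive statistics by time point".

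**The concern.** The two halves of the scoring sentence conflict. The first scores a subscale only when at least two of its items are completed. The second counts a subscale that has one item on the form. A program that follows the text would set Intimacy to missing throughout, and because the second step averages whatever is not missing, it would still return a total with no warning. That total would omit a domain that the SAP says it contains.

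The threshold also matters for the other subscales. Not-applicable answers are not counted, so a two-item subscale with one usable answer would drop out as well. The documents do not map items 1 to 9 to the other four subscales, so they do not show how often this could happen or whether another subscale also has only one item.

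At stake is the score behind a secondary endpoint and its descriptive summaries, and whether two programmers working from this text would obtain the same totals.

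**Working it through.** **Inputs**
- Threshold for scoring a subscale: at least two completed items (SAP 9.3.2).
- Total: 5 × the mean of the non-missing subscale means, over five named subscales (SAP 9.3.2).
- Item values: 1 to 4, with not-applicable answers left out (SAP 9.3.2).
- Items on intimacy or sex: 1 of 10 (Protocol Appendix 15).

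**The stated range.** With every item at 1, all scored subscale means are 1 and the total is 5 × 1 = 5. With every item at 4 it is 5 × 4 = 20. Both hold with or without Intimacy. The 5–20 range is therefore reproduced, but it does not show which rule was meant, and a range check would not reveal the omission.

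**Can Intimacy ever be scored?** Its maximum number of completed items is 1 and the threshold is 2. It cannot be scored for any subject at any visit.

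**Gap at one visit.** Assume that only Intimacy drops out and that the other four subscales are all scored. Let m4 be the mean of those four and I the answer to item 10.
- Literal total: 5 × m4.
- Five-subscale total: 5 × (4 × m4 + I)/5 = 4 × m4 + I.
- Gap, five-subscale minus literal: (4 × m4 + I) − 5 × m4 = I − m4.

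| m4 | Item 10 | Literal | Five-subscale | Gap |
|---|---|---|---|---|
| 3 | 3 | 15 | 15 | 0 |
| 3 | 2 | 15 | 14 | −1 |
| 3 | 1 | 15 | 13 | −2 |
| 4 | 1 | 20 | 17 | −3 |
| 1 | 4 | 5 | 8 | +3 |

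The range spans 20 − 5 = 15 points, so gaps of 1, 2 and 3 points are 6.7%, 13.3% and 20.0% of it. The gap does not depend on how items 1 to 9 map to the four other subscales, provided that all four are scored. A subject who marks item 10 as not applicable has no Intimacy score under either rule, so the two totals agree.

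**Gap in the change score.** The endpoint is a change, so its gap is (change in I) − (change in m4). This is zero when item 10 moves with the rest. If the other subscales stay at 3 and item 10 falls from 4 to 3, the five-subscale total goes from 4 × 3 + 4 = 16 to 4 × 3 + 3 = 15, a change of −1. The literal total stays at 15, a change of 0.

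**If another subscale also has one item.** This is an assumption, because the documents give no map. With subscale sizes 2, 2, 3, 2 and 1, the literal rule leaves four scored subscales. With sizes 2, 3, 3, 1 and 1 it leaves three, and the formulas above no longer apply in general.

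**Reach.** Protocol 6.14.6 states: "Subjects will complete the FOSQ-10 at the Baseline Visit, at the End of Stable Dose Visit, at the End of Double-blind Randomized Withdrawal Visit". It adds open-label extension Weeks 6 and 14 and the end-of-extension or early termination visit. That makes 3 + 3 = 6 scheduled visits scored by this rule.

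**The case against.** The strongest reply is that the exclusion is inferred. SAP 9.3.2 never says that a subscale with one completed item is set to missing, whereas the ESS and IHSS sections (9.1 and 9.2.2) say explicitly when a total is set to missing. The phrase could simply describe when averaging is needed: a lone answer needs no mean and stands as its own score. That reading keeps all five named subscales, and it may well be what was intended.

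It is not written, however. If every lone answer carries through, the threshold has no numerical effect. If only single-item subscales carry through, the SAP has to say so, because a two-item subscale with one usable answer would then be treated differently. Protocol 6.14.6, 9.8.1.3 and 9.9.1.3 give no scoring rule that would settle it.

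A second reply is that the 3-point figure is a gap in level at one visit between extreme and opposite answers, while the endpoint is a change, in which a constant offset cancels. That stands. The 3 points bound the discrepancy in one subject's score at one visit and are not an estimate of bias.

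It is also fair that the consequence is small. The rule is the same in both arms, the open-label use is descriptive, and item answers are collected, so totals can be recomputed.

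**Conclusion.** The point holds. As written, the rule scores at most four of the five subscales that it names, because Intimacy has one item and the threshold requires two. The intended rule was probably at least one completed item, or carry-through for a single-item subscale, but neither is stated.

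The single-visit discrepancy is item 10 minus m4, between −3 and +3 points on the 5–20 scale, on the assumption that only Intimacy drops out and the other four subscales are scored. The effect on the difference between arms depends on whether item 10 changes differently from the other subscales. The documents give no data on that and no sign of a difference between arms.

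Severity is minor. FOSQ-10 lies outside the ESS–PGIc–IHSS testing hierarchy, and SAP 7.4 says: "All other secondary endpoints, subgroup, and sensitivity analyses will be tested without multiplicity adjustments and nominal p-values will be provided". The primary endpoint, the key secondary endpoints, power and family-wise error are unaffected.

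**What to change.** Amend SAP 9.3.2 to say that a single-item subscale takes the value of its completed item. Then settle the threshold for the rest by choosing one of two rules:
- keep the two-item minimum, explicitly for multi-item subscales only; or
- replace it with a minimum of one completed item for all subscales.

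The instrument's scoring instructions should decide between them. Check the scoring program against the amended text.

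This should be done before the database snapshot for the comparative analysis. SAP 5.6 says: "Unblinding will occur after the data extraction is completed". Settling the rule later would mean choosing a scoring method with treatment assignments known.

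The cost is one sentence in the SAP and a check of the program. No new data are needed.
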